8. INVESTIGATIONAL PRODUCT

There are three investigational medicinal products to be studied in HIV-CORE 0052: ChAdOx1.tHIVcons1, MVA.tHIVcons3 and MVA.tHIVcons4. All investigational medicinal products are manufactured under Good Manufacturing Practices and in compliance with European Union GMP guidelines.

8.1 Manufacturing and presentation

8.1.1 *ChAdOx1.tHIVcons1*

ChAdOx1.tHIVcons1 is manufactured by ADVENT s.r.l. registered in Italy, VAT no. IT088464101 [name]. The drug product is formulated as a suspension for injection of intramuscular use. For use in the proposed clinical trial, the viral ChAdOx1.tHIVcons1 drug product will be provided as a sterile virus suspension. It is a slightly opaque frozen liquid supplied at a target concentration of $>1.1 \times 10^{11}$ vp/ml. The fill volume per vial is 0.65 ml.

8.1.2 *MVA.tHIVcons3 and MVA.tHIVcons4*

MVA.tHIVcons3 and MVA.tHIVcons4 are manufactured by IDT Biologika GmbH, [name]. MVA.tHIVcons4 and MVA.tHIVcons3 vaccines are presented as white cloudy solutions, formulated in Tris-saline buffer (10 mM Tris HCl, 140 mM NaCl, pH 7.7) at a concentration of 1.8×10^8 pfu/ml for MVA.tHIVcons4 and 3.4×10^8 pfu/ml for MVA.tHIVcons3. The extractable fill volume is 500 μ l.

8.2 Supply and labelling

All the vaccines will be labelled according to EU requirements for primary and secondary labels.

8.2.1 *ChAdOx1.tHIVcons1*

ChAdOx1.tHIVcons1 has been formulated and vialled under Good Manufacturing Practice conditions at ADVENT s.r.l. registered in Italy, VAT no. IT088464101 [name]. The vaccine will be certified and labelled for the trial by a Qualified Person (QP) before transfer to the clinical site. The ChAdOx1.tHIVcons1 vaccines are supplied in standard glass vials with rubber stoppers and caps.

8.2.2 MVA.tHIVconsV3 and MVA.tHIVconsV4

MVA.tHIVconsV3 and MVA.tHIVconsV4 have been labelled and technically released and vialled by IDT Biologika GmbH, [name]. The vaccines will be certified and labelled for the trial by a Qualified Person (QP) before transfer to the clinical site. The products are supplied in sterile rubber-stopped glass vials.

8.3 Storage

The vaccines are stored at a nominal ≤-65°C in a locked freezer, at the clinical site. All movements of the study vaccines will be documented in accordance with existing standard operating procedures (SOPs). Vaccine accountability, storage, shipment and handling will be in accordance with relevant SOPs and forms.

8.4 Administration

On vaccination day, vaccines will be allowed to thaw to room temperature and will be administered within 1 hour of removal from the freezer. Participants will receive two IM injections with a half dose of ChAdOx1.tHIVconsV1 into each arm at enrolment. Participants in group 2 will receive an additional two IM injections (MVA.tHIVconsV3 into one arm and MVA.tHIVconsV4 into the other arm) at the second vaccination visit. The preferred site of administration is the deltoid muscle, unless contraindicated for any reason. If the administration in one deltoid area is contraindicated, then both vaccinations will be administered in the deltoid region of the other arm. If administration in both arms is contraindicated, then vastus lateralis muscle (anterolateral thigh) of each leg can be used, at the discretion of the investigator. First participants in each group will be observed in the unit for 60 minutes (+/- 5 minutes) after vaccination and all participants will be observed for 30 minutes (+/- 5 minutes). During administration of the investigational products, Advanced Life Support drugs and resuscitation equipment will be immediately available for the management of anaphylaxis. Vaccination will be performed and the IMPs handled according to the relevant SOPs.

8.5 Minimising environmental contamination with genetically modified organisms (GMO)

The study will be performed in accordance with UK Genetically Modified Organisms (Contained Use) Regulations (2014). Approved SOPs will be followed to minimise dissemination of the recombinant

CONFIDENTIAL

vectored vaccine virus into the environment. GMO waste will be inactivated by autoclaving according to approved SOPs.

9. ASSESSMENT OF SAFETY

Safety will be assessed by the frequency, incidence and nature of AEs and SAEs arising during the study.

9.1 Definitions

9.1.1 *Adverse Event (AE)*

An AE is any untoward medical occurrence in a volunteer, which may occur during or after the administration of an IMP and does not necessarily have a causal relationship with the intervention. An AE can therefore be any unfavourable and unintended sign (including an abnormal laboratory finding), symptom or disease temporally associated with the study intervention, whether or not considered related to the study intervention.

9.1.2 *Adverse Reaction (AR)*

An AR is any untoward or unintended response to an IMP. This means that a causal relationship between the IMP and an AE is at least a reasonable possibility, i.e., the relationship cannot be ruled out. All cases judged by the reporting medical Investigator as having a reasonable suspected causal relationship to an IMP (i.e. possibly, probably or definitely related to an IMP) will qualify as an AR.

AEs that may be related to the IMP are listed in the Investigator's Brochure for each product.

9.1.3 *Serious Adverse Event (SAE)*

A SAE is an AE that results in any of the following outcomes, whether or not considered related to the study intervention.

- Death
- Life-threatening event (i.e., the volunteer was, in the view of the Investigator, at immediate risk of death from the event that occurred). This does not include an AE that, if it occurred in a more severe form, might have caused death.
- Persistent or significant disability or incapacity (i.e., substantial disruption of one's ability to carry out normal life functions).
- Hospitalisation, regardless of length of stay, even if it is a precautionary measure for continued observation. Hospitalisation (including inpatient or outpatient hospitalisation for

an elective procedure) for a pre-existing condition that has not worsened unexpectedly does not constitute a serious AE.

- An important medical event (that may not cause death, be life threatening, or require hospitalisation) that may, based upon appropriate medical judgment, jeopardise the volunteer and/or require medical or surgical intervention to prevent one of the outcomes listed above. Examples of such medical events include allergic reaction requiring intensive treatment in an emergency room or clinic, blood dyscrasias, or convulsions that do not result in inpatient hospitalisation.
- Congenital anomaly or birth defect.

“Severe” is often used to describe intensity of a specific event, which may be of relatively minor medical significance. “Seriousness” is the regulatory definition supplied above.

9.1.5 *Serious Adverse Reaction (SAR)*

An AE (expected or unexpected) that is both serious and, in the opinion of the reporting Investigator or Sponsors, believed to be possibly, probably or definitely due to an IMP or any other study treatments, based on the information provided.

9.1.6 *Suspected Unexpected Serious Adverse Reaction (SUSAR)*

An SAR, the nature and severity of which is not consistent with the information about the medicinal product in question set out in the IB.

9.2 Expectedness

No IMP related SAEs are expected in this study. All SARs will therefore be reported as SUSARs.

9.3 Causality Assessment

For every AE, an assessment of the relationship of the event to the administration of the vaccine will be undertaken by the PI or a delegated clinician. An interpretation of the causal relationship of the intervention to the AE in question will be made, based on the type of event; the relationship of the event to the time of vaccine administration; and the known biology of the vaccine therapy. Alternative causes of the AE, such as the natural history of pre-existing medical conditions, concomitant therapy, other risk factors and the temporal relationship of the event to vaccination will

be considered and investigated. Causality assessment will take place during planned safety reviews, interim analyses (e.g. if a holding or stopping rule is activated) and at the final safety analysis, except for SAEs, which should be assigned by the reporting investigator.

Table 4. Guidelines for assessing the relationship of vaccine administration to an AE.

0	No Relationship	No temporal relationship to study product and Alternate aetiology (clinical state, environmental or other interventions); and Does not follow known pattern of response to study product
1	Unlikely	Unlikely temporal relationship to study product and Alternate aetiology likely (clinical state, environmental or other interventions) and Does not follow known typical or plausible pattern of response to study product.
2	Possible	Reasonable temporal relationship to study product; or Event not readily produced by clinical state, environmental or other interventions; or Similar pattern of response to that seen with other vaccines
3	Probable	Reasonable temporal relationship to study product; and Event not readily produced by clinical state, environment, or other interventions or Known pattern of response seen with other vaccines
4	Definite	Reasonable temporal relationship to study product; and Event not readily produced by clinical state, environment, or other interventions; and Known pattern of response seen with other vaccines

9.4 Reporting procedures for all Adverse Events (see local SOP for AE reporting)

All local and systemic AEs occurring in the 28 days following each vaccination observed by the Investigator or reported by the volunteer, whether or not attributed to study medication, will be

recorded. Recording and reporting of all AEs will take place as detailed in SOP VC027 Adverse Event Data Collection and Analysis. All AEs that result in a volunteer's withdrawal from the study will be followed up until a satisfactory resolution occurs, or until a non-study related causality is assigned (if the volunteer consents to this). SAEs will be collected throughout the entire trial period (D140).

9.4.1 *Reporting procedures for Serious AEs (see local SOP for Safety Reporting)*

In order to comply with current regulations on SAE reporting to regulatory authorities, the event will be documented accurately and notification deadlines respected. SAEs will be reported on the SAE forms to members of the study team immediately when the Investigators become aware of their occurrence, as described in SOP OVC005 Safety Reporting for CTIMPs. Copies of all reports will be forwarded for review to the CI (as the Sponsor's representative) within 24 hours of the Investigator being aware of the suspected SAE. The local safety monitor (LSM) will be notified of SAEs that are deemed possibly, probably or definitely related to study interventions; the LSM will be notified immediately (within 24 hours) of the Investigators' being aware of their occurrence. SAEs will not normally be reported immediately to the ethical committee(s) unless there is a clinically important increase in occurrence rate, an unexpected outcome, or a new event that is likely to affect safety of trial volunteers, at the discretion of the CI, following the advice of the LSM. In addition to the expedited reporting above, all SAEs will be reported in the annual Development Safety Update Report (DSUR) report. Hospitalisations for elective procedures that are planned prior to enrolment into the study will not be reported as SAEs.

9.4.2 *Reporting Procedures for SUSARS*

The CI will report all SUSARs to the MHRA and ethical committee(s) within required timelines (15 days for all SUSARs, unless fatal or life threatening in which case 7 days, with a final report within a further 8 days (total 15)). The CI will also inform all Investigators concerned of relevant information about SUSARs that could adversely affect the safety of participants. All SUSARs and deaths occurring during the study will be reported to the Sponsor. For all deaths, available autopsy reports and relevant medical reports will be made available for reporting to the relevant authorities.

9.4.3 Development Safety Update Report

A Development Safety Update Report (DSUR) will be submitted to the competent authority and ethical committee within 60 days of the anniversary of the first approval date from the regulatory authority for each IMP.

9.5 Assessment of severity

The severity of clinical and laboratory AEs will be assessed according to the scales in the Division of AIDS (DAIDS) Table for Grading the Severity of Adult and Pediatric Adverse Events (Corrected Version 2.1, July 2017), attached as Appendix A to this protocol.

9.6 Procedures to be followed in the event of abnormal findings

Eligibility for enrolment in the trial in terms of laboratory findings will be assessed as detailed in Appendix A. Abnormal clinical findings from medical history, examination or blood tests will be assessed as to their clinical significance throughout the trial. Laboratory AEs will be assessed using the site-specific tables in the TMF. If a test is deemed clinically significant, it may be repeated, to ensure it is not a single occurrence. If a test remains clinically significant, the volunteer will be informed and appropriate medical care arranged as appropriate and with the permission of the volunteer. Decisions to exclude the volunteer from enrolling in the trial or to withdraw a volunteer from the trial will be at the discretion of the Investigator.

9.7 Interim Safety Reviews

The safety profile of the IMP will be assessed on an on-going basis by the Investigators with communication to the LSM as necessary. The CI and other relevant Investigators (as per the trial delegation log) will also review safety issues and SAEs as they arise.

9.8 Local Safety Monitor

[name], a Clinical Tutor in Medicine, Honorary Consultant Physician and Director, Centre for Tropical Medicine at the University of Oxford will be appointed as an independent Local Safety monitor (LSM) to provide real-time safety oversight. The LSM will review SAEs deemed possibly, probably or definitely related to study interventions. The LSM will be notified within 24 hours of the investigators' being aware of their occurrence. The LSM has the power to terminate the study if

deemed necessary following a study intervention-related SAE. . All correspondence between investigator and LSM will be conveyed by the investigator to the trial Sponsor.

The LSM may be contacted for advice and independent review by the investigator or trial Sponsor in the following situations:

- Following any SAE deemed to be possibly, probably, or definitely related to a study intervention.
- Any other situation where the Investigator or trial sponsor feels independent advice or review is important.

9.8.1 *Safety Profile Review*

The safety profile will be assessed on an on-going basis by the Investigators, and at the time points dictated by the staggered enrolment. In addition, the LSM will perform independent external safety reviews after the first 5 volunteers reach day 14 and day 63. The CI and relevant Investigators (as per the trial delegation log) will also review safety issues and SAEs as they arise.

9.9 Safety Holding Rules

Safety holding rules have been developed considering the fact that this is a phase 1 study. Solicited AEs are those listed as foreseeable in the Investigator's Brochure for each product, occurring within the first 7 days after vaccination (day of vaccination and six subsequent days). 'Unsolicited AEs' are AEs other than the foreseeable AEs occurring within the first 28 days after vaccination.

9.9.1 *Re-vaccination excluding criteria*

The following AEs associated with vaccine immunisation constitute absolute contraindications to further administration of vaccine. If any of these events occur during the study, the subject must be withdrawn and followed until resolution of the event, as with any AE.

- Anaphylactic reaction following administration of the vaccine
- Pregnancy

The following AEs constitute contraindications to administration of vaccine at that point in time; if any one of these AEs occurs at the time scheduled for vaccination, the subject may be vaccinated at

a later date, or withdrawn at the discretion of the CI. The subject must be followed until resolution of the event as with any AE.

- Acute disease at the time of vaccination (defined as the presence of a moderate or severe illness with or without fever). All vaccines can be administered to persons with a minor illness such as diarrhoea, mild upper respiratory infection with or without low-grade febrile illness, i.e. temperature of $< 37.7^{\circ}\text{C} / 99.9^{\circ}\text{F}$.
- Temperature of $\geq 37.7^{\circ}\text{C} (99.9^{\circ}\text{F})$ at the time of vaccination.

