- True abstinence, when this is in line with the preferred and usual lifestyle of the subject
(Periodic abstinence and withdrawal are not acceptable methods of contraception)

Barrier methods for the purposes of contraception (condom or occlusive cap with spermicide) for female volunteers are not acceptable as they are not considered “highly effective” (i.e. <1% failure rate).

6.3.4 *Temporary Exclusion Criteria*

The following AEs constitute contraindications to administration of vaccine at that point in time; if any one of these AEs occur at the time scheduled for vaccination, the subject may be vaccinated at a later date, or withdrawn at the discretion of the CI. The subject must be followed until resolution of the event as with any AE:

- Acute disease at the time of vaccination. (Acute disease is defined as the presence of a moderate or severe illness with or without fever). Most vaccines can be administered to persons with a minor illness such as diarrhoea, mild upper respiratory infection with no fever or low-grade febrile illness (i.e. temperature of ≤ 37.5 °C/99.5 °F) at the discretion of the reviewing clinician. The decision to proceed with vaccination in this situation should be clearly explained in the CRF with careful consideration given to causality assignment of AEs which occur during the post vaccination period.
- Temperature of >37.5 °C (99.5 °F) at the time of vaccination.

6.3.5 *Prevention of 'Over Volunteering'*

Volunteers will be excluded from the study if they are concurrently involved in another trial. In order to ensure this, volunteers will be asked to provide their National Insurance or Passport number (if they are not entitled to a NI number) and will be registered on a national database of participants in clinical trials (www.tops.org.uk). They will not be enrolled if found to be actively registered on another trial.

6.3.6 *Withdrawal of Volunteers*

In accordance with the principles of the current revision of the Declaration of Helsinki and any other applicable regulations, a volunteer has the right to withdraw from the study at any time and for any reason, and is not obliged to give his or her reasons for doing so. The Investigator may withdraw the volunteer at any time in the interests of the volunteer's health and well-being. In addition, the volunteer may be withdrawn by the investigator for any of the following reasons:

- Administrative decision by the Investigator.

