- Ineligibility (either arising during the study or retrospectively, having been overlooked at screening).
- Significant protocol deviation.
- Volunteer non-compliance with study requirements.
- An AE, which requires discontinuation of the study involvement or results in inability to continue to comply with study procedures.

The reason for withdrawal will be recorded in the CRF. If withdrawal is due to an AE, appropriate follow-up visits or medical care will be arranged, with the agreement of the volunteer, until the AE has resolved, stabilised or a non-trial related causality has been assigned. Any volunteer who is withdrawn from the study may be replaced, if that is possible within the specified time frame. The Local Safety Monitor (LSM) may recommend withdrawal of volunteers; however, the final decision will be made by the CI. Any volunteer who fails to attend for two or more follow-up visits during the study, despite active attempts to contact volunteer by trial team, will be deemed to have withdrawn from the study.

If a volunteer withdraws from the study, blood samples collected before their withdrawal from the trial will be used/ stored unless the volunteer specifically requests otherwise.

Participants who receive another adenoviral vectored vaccine as part of the national Covid-19 immunisation programme within 3 months from ChAdOx1.tHIVconsV1 will remain in the study, but data might be analysed separately from the rest of the cohort.

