9.10.2 Criteria for Temporary Halt of Vaccinations in All Volunteers

All vaccinations as part of this study will be suspended (i.e. no further vaccinations will be given to any participant) if any of the following criteria arise:

1. One volunteer experiences an SAE that is possibly, probably or definitely related to the investigational product(s).
2. Two unforeseen severe AEs occur which are deemed clinically significant by the LSM. (All severe AEs will be reviewed in the study.)
3. One volunteer experiences injection site ulceration, sterile abscess or necrosis possibly, probably or definitely associated with vaccine administration.
4. One volunteer experiences a severe allergic reaction, such as laryngospasm, bronchospasm or anaphylaxis, possibly, probably or definitely associated with vaccine administration.
5. One volunteer experiences a life-threatening event or death regardless of the causality.

Vaccinations may be recommenced only if it is deemed safe to recommence by the LSM, the MHRA, the ethics committee and the study investigators following the procedures below. Procedures to follow after discontinuing vaccinations:

If vaccinations are suspended MHRA and REC will be notified within 15 days with a substantial amendment, using the notification of amendment form, clearly explaining the reason for the halt of vaccinations. In addition, the Investigators will request a review by the LSM, to be held within two business days of the Investigators learning of the event. No additional vaccinations will be given until the opinion of the LSM has been sought. However, all volunteers will remain in the study for

immunological and safety follow up. To restart vaccinations, a further request as a substantial amendment, providing evidence that it is safe to restart the trial should be made to MHRA and REC.

In addition to these pre-defined criteria, the study can be put on hold upon advice of the Local Safety Monitor, CI, Study Sponsor, Regulatory Authority, or Ethical Committee(s), for any single event or combination of multiple events which, in their professional opinion, jeopardises the safety of the participants or the reliability of the data.

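### Outside pregnancy and a trial-wide halt, the protocol does not separate stopping vaccine from leaving the study, so a dosed volunteer withdrawn by the investigator has no scheduled contact to complete the safety windows

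*Combined protocol and SAP*

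**What the plan says.** **Permanent contraindications (9.9.1).** After vaccine-associated anaphylaxis or pregnancy, "the subject must be withdrawn and followed until resolution of the event, as with any AE".

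**Temporary contraindications (6.3.4, repeated in 9.9.1).** With acute illness or fever at a vaccination visit, "the subject may be vaccinated at a later date, or withdrawn at the discretion of the CI". Section 9.9.1 gives the same two options: vaccination at "a later date, or withdrawn at the discretion of the CI".

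**Withdrawal (6.3.6).** Besides acting for the volunteer's health and well-being, "the volunteer may be withdrawn by the investigator for any of the following reasons": administrative decision, ineligibility, significant deviation, non-compliance, or an AE. If an AE is the cause, follow-up is arranged "until the AE has resolved, stabilised or a non-trial related causality has been assigned". The section adds: "Any volunteer who is withdrawn from the study may be replaced, if that is possible within the specified time frame".

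**Early Termination (Tables 2a and 2b, footnote 2; 7.4.4).** Procedures are those of the final visit, week 16 for Group 1 and week 20 for Group 2.

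**Collection windows (9.4).** AEs are recorded for 28 days after each vaccination. For SAEs: "SAEs will be collected throughout the entire trial period (D140", where D140 is Group 2's final visit and Group 1's is D112.

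**Where stopping vaccine is already kept apart from leaving.** Section 6.5 stops vaccine in pregnancy and continues clinical safety follow-up with consent. Section 9.10.2 says that after a halt "all volunteers will remain in the study for" immunological and safety follow-up. Section 6.3.6 also keeps in the study anyone given another adenoviral vaccine within three months.

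**The concern.** Illness at the second dose, a deviation or late-found ineligibility is a reason to stop dosing, or to question some data. None of these is a reason to stop asking about safety after a dose already given. The text offers no option to skip the dose and stay on the schedule, and 6.3.6 treats withdrawal as departure from the study, with possible replacement.

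Two primary endpoints have fixed windows: Grade 3 or 4 unsolicited AEs to 28 days after the final vaccination, and vaccine-related SAEs throughout the study. Section 9.4 states the collection periods without exception, but no visit or call is scheduled to deliver them once the investigator has withdrawn someone. In a first-in-human trial of 13 people, a later event in a dosed volunteer could be missed unless that person volunteers it.

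**Working it through.** The plan has no figure to reproduce here. The check is a reading of each route out of vaccination, followed by simple counts.

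**1. What follows each route**

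| Route | Follow-up after it |
|---|---|
| Pregnancy | Safety follow-up continues (6.5) |
| Vaccine-related anaphylaxis | Halt criterion 4; all volunteers stay in follow-up (9.10.2) |
| Illness or fever at second dose, volunteer withdrawn | Early Termination visit; follow-up of that illness |
| AE-led withdrawal (6.3.6) | Early Termination visit; follow-up of that AE |
| Administrative, ineligibility, deviation, non-compliance (6.3.6) | Early Termination visit only |

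The first two rows are covered, although 9.9.1 still says these volunteers must be withdrawn, which agrees with 6.5 and 9.10.2 only if it means withdrawn from vaccination. The last three rows are the gap.

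**2. How rare the anaphylaxis route is.** Section 5.6 puts anaphylaxis below 1 in 1,000 people. Using that bound, the chance of any case among 13 volunteers is 1 − 0.999^13 = 0.0129, at most 1.3%.

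**3. Withdrawal at the scheduled D28 dose (Group 2 only; Group 1 has one dose)**
- AE window of the first dose: 28 − 28 = 0 days left, so it has closed.
- SAE window: 140 − 28 = 112 days left, and 112/140 = 80%.
- Later scheduled contacts no longer made: D29, D35, D42, D56, D84 and D140, six in all. Several of these exist because of the boost.

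**4. Withdrawal between visits after the first dose.** The documents give no day, so D7 to D21 is assumed.
- AE days left: 28 − 7 = 21, down to 28 − 21 = 7.
- SAE days left, Group 1: 112 − 7 = 105, down to 112 − 21 = 91.
- SAE days left, Group 2: 140 − 7 = 133, down to 140 − 21 = 119.

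**5. The baseline for these counts.** Retained volunteers also have long intervals without contact.
- Group 1, D28 to D112: 84 days, and 84/112 = 75%.
- Group 2, D84 to D140: 56 days.

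For a retained volunteer, the enquiry at the end of the interval recovers what happened in it. For a withdrawn volunteer, no such enquiry follows. The loss is therefore the later retrospective enquiry, and the day counts show only the period it would have covered.

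**The case against.** **The protocol already intends to retain people.** Sections 6.5, 9.10.2 and the last paragraph of 6.3.6 all keep volunteers in follow-up despite a dosing problem. In 9.9.1, withdrawal can be read as withdrawal from vaccination, given that subsection's title. This stands for pregnancy and anaphylaxis. A reader might infer from 9.9.1 that a volunteer with anaphylaxis drops out of safety follow-up; the documents do not support that, because the same event triggers 9.10.2. It does not rescue the other routes, where no retaining text applies.

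**There are other reporting channels.** The e-diary takes solicited and unsolicited AEs for up to 28 days after a dose (11.1), and volunteers can reach the on-call study physician at any hour (section 7.4.2, under Vaccination). This softens the AE part. But nothing says that the diary continues after withdrawal, it does not reach later SAEs, and the on-call line depends on the volunteer calling.

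**The second-dose case is narrow.** Later vaccination is offered first, and withdrawal is at the chief investigator's discretion. That stands; only late SAE capture is affected.

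**Section 10 might seem to leave the volunteer uncounted.** It does not: everyone with at least one vaccination is included. What is open is how a shortened, event-free window is treated beside the rule excluding missing data. Section 10 defers to an agreed Statistical Analysis Plan that is not among the documents. The choice would move little in Group 2: with no events, the exact 95% upper limit, 1 − 0.025^(1/n), is 30.8% for 0/10 and 33.6% for 0/9. In Group 1 it is 70.8% for 0/3 and 84.2% for 0/2, both too wide to inform anything.

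**The SOPs cited in 9.4 may add follow-up.** They may; they are also not among the documents.

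**Conclusion.** The point holds in limited form and is minor. For a dosed volunteer withdrawn by the investigator, outside pregnancy and a trial-wide halt, nothing beyond one Early Termination visit and follow-up of a causal AE is scheduled to complete the windows behind two primary endpoints.

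A reader might take the 80% figure at D28 to mean that 80% of SAE information is lost. The documents do not support that, since retained volunteers have intervals of 84 days (Group 1) and 56 days (Group 2) without contact. Nor is a primary endpoint shown to be compromised: the safety analysis is mainly descriptive, the halting rules act on single events or, for unforeseen severe AEs, on two, and the protocol expects little missing data.

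The conclusion rests on three assumptions: that withdrawal in 6.3.4, 6.3.6 and the temporary-contraindication part of 9.9.1 means leaving the study; that the final vaccination of a withdrawn volunteer is the last dose received; and that the unseen SOPs do not already require continued contact. The frequency cannot be estimated, because the documents give no withdrawal rate.

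**What to change.** Leave the conditions that stop vaccination as they are, and change what follows.

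- **6.3.4 and 9.9.1:** for a volunteer who has already had a dose, replace withdrawal with *receives no further study vaccine and, with consent, remains in safety follow-up to the final visit*. This also brings 9.9.1 into line with 6.5 and 9.10.2.
- **6.3.6 and 9.4:** state that dosed volunteers withdrawn by the investigator continue, with consent and by phone if needed, AE collection to 28 days after the last dose received and SAE collection to D112 (Group 1) or D140 (Group 2).
- **Statistical Analysis Plan:** if not already there, say how a shortened window is counted and report how many there are.

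The volunteer's own right to withdraw is untouched. The rule on two or more missed visits can stay, because contact has already been attempted there. The cost is wording in four sections and a few phone contacts per affected volunteer.
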